### **7.3 WEIGHT-ADJUSTED DOSE OF RAPASTINEL**

For the OLTP, the dose of rapastinel will be divided by the corresponding patient's weight assessed at Visit 1 and summarized descriptively overall for the Open-label Safety Population.

For the DBTP, the dose of rapastinel will be divided by the corresponding patient's weight assessed at Visit 18 and summarized descriptively by treatment group for the Double-blind Safety Population.

## **8.0 EFFICACY ANALYSES**

All efficacy analyses for the OLTP will be performed using the Open-label ITT Population. All efficacy analyses for the DBTP will be performed using the Double-blind mITT Population. The baseline Day 0 assessment of the lead-in study will be used as the baseline for the OLTP. The Day 0 assessment is the last non-missing assessment before the first dose of Double-blind IP during the placebo lead-in period of their respective lead-in study. The last non-missing assessment before the first dose of Double-blind IP in the DBTP will be used as the baseline for the DBTP. All statistical tests will be 2-sided hypothesis tests performed at the 5% level of significance and all CIs will be 2-sided 95% CIs, unless stated otherwise.

The rater-administered MADRS will be used when deriving endpoints for analyses. The computer-administrated MADRS scores will be provided in a listing.

## **8.1 PRIMARY EFFICACY ANALYSIS**

The primary efficacy parameter is the time to first relapse. Relapse during the DBTP is defined as meeting any of the following criteria:

- MADRS total score  $\geq 18$  at 2 consecutive assessments. The 2 MADRS assessments must occur on different calendar dates
- $\geq 2$  increase in CGI-S score compared with that obtained at randomization
- Risk of suicide as determined by the investigator
- Need for hospitalization due to worsening of depression as determined by the investigator
- Need for alternative treatment of depressive symptoms as determined by the investigator

Further details on the derivation of the relapse criterion are provided in section 15.3.

The primary endpoint is the time to first relapse during the first 52 weeks of the DBTP, defined as relapse date – randomization date + 1. Patients who do not meet the above relapse criteria during the first 52 weeks of the DBTP will be censored at 52 weeks or the time of completion or discontinuation from the study, whichever is earlier.

The primary efficacy analysis is to evaluate the time to first relapse in MDD patients who are stable responders to open-label treatment with rapastinel for MDD.

The primary null hypothesis is that the distribution of the time to first relapse for each of the rapastinel 450 mg weekly and 450 mg biweekly treatment groups is not different from that for the placebo treatment group. The primary alternative hypothesis is that the distribution of the time to first relapse for either of the rapastinel 450 mg weekly and 450 mg biweekly treatment groups is different from that for the placebo treatment group.

The hypothesis testing will compare the time to first relapse between each rapastinel group and the placebo group using the log-rank test for the Double-blind mITT Population. Estimates of the hazard ratio and 95% CIs will be based on the Cox proportional hazards model with treatment group as an explanatory variable. The Kaplan-Meier estimates for the cumulative distribution of the relapse rate for each treatment group will be provided. The proportion of patients who relapse, the Kaplan-Meier estimate of the median, first quartile and third quartile of the time to first relapse and corresponding 95% CI for the median will be presented for each treatment group. Plots of the Kaplan-Meier estimate of the distribution of the time to first relapse will also be provided for each treatment group. The primary reason for relapse, as collected on the *Relapse CRF*, will be tabulated by treatment group.

Three sensitivity analyses will be performed to assess the robustness of the primary analysis results to the possible violation of the noninformative censoring assumption. The first sensitivity analysis assumes that patients who discontinued without meeting any of the relapse criteria during the first 52 weeks of the DBTP relapsed instead of being censored. The second sensitivity analysis will be based on the delta-adjusted method examined by Zhao et al (2014). The third sensitivity analysis is an extension of the placebo-based pattern mixture model proposed by Lu (2014, 2015). The placebo-based pattern mixture model assumes that patients who discontinued from the rapastinel treatment groups would have disease progression after discontinuation similar to that of placebo. The extended placebo-based pattern mixture model uses a sensitivity parameter to characterize the gradual deviation from the noninformative censoring underlying the primary analysis toward the informative censoring underlying the placebo-based pattern mixture model. The extended placebo-based pattern mixture model sensitivity analysis for time-to-event data is described as follows:

Let  $h_0(t)$  denote the baseline hazard function associated with the placebo group. Let  $\beta_1$  and  $\beta_2$  denote the treatment effects in terms of log hazard ratios under noninformative censoring for rapastinel 450 mg weekly versus placebo and rapastinel 450 mg biweekly versus placebo, respectively. The hazard functions associated with the rapastinel 450 mg weekly and 450 mg biweekly groups under noninformative censoring are thus given by  $h_1(t) = h_0(t) \exp(\beta_1)$  and  $h_2(t) = h_0(t) \exp(\beta_2)$ , respectively. Consider the extended placebo-based pattern mixture model sensitivity analysis. For the placebo group, we assume that patients with premature discontinuation would have comparable experience after discontinuation to their counterparts without premature discontinuation. For the rapastinel treatment groups, each dropout timepoint for rapastinel patients defines a missing data pattern, and we assume that patients with premature discontinuation would have disease progression after discontinuation somewhere between their counterparts without premature discontinuation and patients in the placebo group. Specifically, we assume that  $h_1(t) = h_0(t) \exp((1-\phi)\beta_1)$  and  $h_2(t) = h_0(t) \exp((1-\phi)\beta_2)$  for  $t > C$ , where  $C$  denotes the time of premature discontinuation. The sensitivity parameter  $\phi \in [0,1]$  characterizes the gradual deviation from the noninformative censoring with  $\phi = 0$  toward the informative censoring underlying the placebo-based pattern mixture model with  $\phi = 1$ . A multiple imputation approach will be used to implement the extended placebo-based pattern mixture model.

Technical details for the implementation of the sensitivity analyses are provided in [APPENDIX I](#).

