## **2.0 INTRODUCTION**

This Statistical Analysis Plan (SAP) describes the methodology that will be used to summarize the statistical analyses of the efficacy and safety data for the final protocol Amendment 2 of Study RAP-MD-04 (version dated 13 Nov 2018).

Study RAP-MD-04 is a multicenter, double-blind, randomized, placebo-controlled, parallel-group study to evaluate the efficacy, safety, and tolerability of rapastinel as long-term maintenance treatment for patients with major depressive disorder (MDD) who completed 1 of the rapastinel lead-in studies (RAP-MD-01, RAP-MD-02, or RAP-MD-03). While the protocol was written to accommodate the potential recruitment of *de novo* patients, there were no *de novo* patients enrolled. Consequently, all analysis in this document pertains specifically to roll-over patients only.

The study will be conducted for the roll-over patients in the following periods:

- An 8- to 16-week, open-label treatment period (OLTP) where patients receive rapastinel 450 mg IV weekly
- A randomized, double-blind treatment period (DBTP) of at least 26 weeks (and up to 104 weeks) where patients are randomized 1:1:1 to either rapastinel 450 mg weekly, rapastinel 450 mg biweekly or placebo
- A 2-week safety follow-up period (for patients who do not enter the RAP-MD-06 extension study only)

In order for patients to transition from the OLTP and be randomized into the DBTP, the patient must meet the stable responder criterion sometime after 8 weeks (and up to 16 weeks) during the OLTP. A patient will be considered a stable responder upon achieving both criteria (1) and (2) below:

- 1) An observed Montgomery-Asberg Depression Rating Scale (MADRS) total score  $\leq 12$  with no more than one modest MADRS excursion (MADRS total score  $> 12$  but  $\leq 16$ ) for at least 6 consecutive weeks.
- 2) An observed MADRS total score  $\leq 12$  for at least 2 consecutive visits prior to randomization.

To meet these criteria a patient must have no missing MADRS assessments within the last 6 consecutive weeks prior to randomization.

The OLTP starts with the first dose of open-label treatment and ends with 1 of the following: the last scheduled assessment at the Visit 122/Early Termination for patients who do not enter the DBTP; the first dose of double-blind treatment for patients who enter the DBTP.

[figure not shown]

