## 8.2 SECONDARY EFFICACY ANALYSIS

The secondary efficacy endpoint is the time to first relapse during the entire DBTP, defined as the number of days from the randomization date to the relapse date during the entire DBTP. For patients who did not meet the relapse criteria during the DBTP, their time to relapse will be censored at the time of completion or discontinuation from the study. The same analysis method for the primary endpoint will be applied to the secondary endpoint.

In order to control the overall Type I error rate for the primary and secondary hypotheses, the following sequential testing procedure will be implemented in the following order:

- 1) The comparison of time to relapse during the first 52 weeks between rapastinel 450 mg weekly and placebo
- 2) The comparison of time to relapse during the entire DBTP between rapastinel 450 mg weekly and placebo
- 3) The comparison of time to relapse during the first 52 weeks between rapastinel 450 mg biweekly and placebo
- 4) The comparison of time to relapse during the entire DBTP between rapastinel 450 mg biweekly and placebo

Each of the 4 hypothesis tests above will be implemented at the 2-sided 0.05 significance level. A given hypothesis test will be carried out only when each of the preceding hypothesis tests have concluded rejection of the null hypothesis at the 0.05 significance level. In the event a given hypothesis test fails to reject its null hypothesis at the 0.05 significance level, the conclusion for the subsequent hypotheses not tested is to not reject their respective null hypotheses. This testing strategy will control the overall Type I error rate at 0.05 significance level.

*REDACTED*

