**15.11 STRATIFICATION HANDLING CONVENTION**

Stratification is not being implemented in this study.

RESTRUCTURED

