**16.0**

**CHANGES TO ANALYSES SPECIFIED IN PROTOCOL**

There are no changes to the analyses specified in the final protocol Amendment 2 (version dated 06 Nov 2018). While there are analyses for endpoints collected during the OLTP that are with respect to Day 0 of the lead-in studies, it was necessary not to explicitly mention this fact in the RAP-MD-04 protocol Amendment 2 in order to protect restricted information pertaining to RAP-MD-01/02/03.

RESTRICTED

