## **18.0**

## **APPENDICES**

### **APPENDIX I. TECHNICAL DETAILS FOR THE IMPLEMENTATION OF THE EXTENDED PLACEBO-BASED PATTERN MIXTURE MODEL VIA MULTIPLE IMPUTATION**

The following steps will be taken to implement the extended placebo-based pattern mixture model via multiple imputation:

1. Carry out a Bayesian analysis for the Cox proportional hazards model with treatment group as an explanatory variable and with piecewise constant baseline hazard function. Let  $h_0(t; \lambda) = \sum_{j=1}^J \lambda_j I(a_{j-1} \leq t < a_j)$  denote the piecewise constant baseline hazard function, where  $a_0 = 0 < a_1 < \dots < a_{J-1} < a_J = \infty$  denotes a partition of the time axis. The cut points are chosen to have an approximately equal number of events in each interval. The number of intervals with constant baseline hazard rates,  $J$ , is set to strike a balance between the approximation to the unknown underlying baseline hazard function and the number of events in each interval. The hazard function for patient  $i$  is  $h(t | X_i; \theta) = h_0(t; \lambda) \exp(\beta_1 X_{i1})$ , where  $X_{i1} = 1$  if patient  $i$  is in the rapastinel group.
2. Take a posterior draw of the model parameters,  $\tilde{\theta} = (\tilde{\lambda}, \tilde{\beta})$ , from the Bayesian analysis.
3. For a patient who prematurely discontinued without meeting any of the relapse criteria during the DBTP, impute the time to relapse after discontinuation,  $T_i$ , under the extended placebo-based pattern mixture model with sensitivity parameter  $\phi$ , by equating the conditional survival probability at  $T_i$  given that the patient discontinued at  $C_i$  to a uniform random variable  $U_i$ , that is,

[figure not shown]
$$\exp\left\{-\int_{C_i}^{T_i} h_0(t; \tilde{\lambda}) e^{(1-\phi)(\tilde{\beta}_1 X_{i1})} dt\right\} = U_i.$$

[figure not shown]
This equation can be easily solved by noting that the baseline hazard function  $h_0(t; \lambda)$  is piecewise constant.

4. If the imputed event time exceeds the planned follow-up time for the patient, we manage the patient as having no event by the end of the planned follow-up time. Thus, the imputed complete data set has no patients with premature discontinuation and has only administrative censoring at the planned follow-up time.

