5. Apply the primary analysis model to the complete data set to obtain the parameter estimates and associated covariance matrix for a single imputation. The parameters are the log-rank test statistics for the log-rank test, and the log hazard ratios for the Cox model with treatment group as an explanatory variable.
6. Repeat Step 2 through Step 5 for  $m$  times to generate  $m$  sets of imputed complete-data parameter estimates and associated covariance matrices. Use the SAS procedure MIANALYZE to combine results from  $m$  imputed data sets and draw inference about the treatment effects of both rapastinel groups versus placebo.
7. Vary the value of the sensitivity parameter  $\phi \in \{0, 0.2, 0.4, 0.6, 0.8, 1\}$  in Step 3 to assess the robustness of the primary analysis results to the possible violation of the noninformative censoring assumption toward the informative censoring underlying the placebo-based pattern mixture model.

RESTRICTED

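### Should the relapse hazard ratio also be adjusted for MADRS at the start of the double-blind period?

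*SAP*

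**What the plan says.** Section 8.1 compares each rapastinel group with placebo by a log-rank test. The accompanying estimate has treatment as its only stated term: "Estimates of the hazard ratio and 95% CIs will be based on the Cox proportional hazards model with treatment group as an explanatory variable".

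The same choice recurs wherever relapse is analysed:

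- Section 8.2: "The same analysis method for the primary endpoint will be applied to the secondary endpoint".
- Appendix I, step 1 (imputation model): "Bayesian analysis for the Cox proportional hazards model with treatment group as an explanatory variable".
- Appendix I, step 5 (analysis of each imputed data set): "log hazard ratios for the Cox model with treatment group as an explanatory variable".
- Section 15.11: "Stratification is not being implemented in this study".
- Section 16.0 reports no departure from the protocol: "There are no changes to the analyses specified in the final protocol Amendment 2".

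The covariate in question is available. Section 8.0 defines it: "The last non-missing assessment before the first dose of Double-blind IP in the DBTP will be used as the baseline for the DBTP". Section 2.0 makes it close to complete for everyone randomised: "To meet these criteria a patient must have no missing MADRS assessments within the last 6 consecutive weeks prior to randomization".

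**The concern.** Patients enter the double-blind period with a MADRS total of 12 or less, and one of the five relapse criteria is a total of 18 or more at two consecutive assessments. A patient entering at 12 is nearer that line than one entering at 2, so the entry score could well predict relapse. Randomisation does not balance it by stratification. The three sensitivity analyses in Section 8.1 all concern informative censoring, so none addresses baseline imbalance.

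If the arms differed by chance in residual symptoms, the unadjusted HR would move with that difference. Without a planned adjusted estimate, any later adjustment would be post hoc. A supportive Cox model with baseline MADRS would need no new data. It could be expected to show how much of the observed effect reflects imbalance, and perhaps to add precision.

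**Working it through.** **1. Is the unadjusted analysis adequate as planned?** Inputs from Section 13.0: 200 per group, placebo relapse 19% per 26 weeks, dropout 20% per 26 weeks, HR 0.475, two-sided 0.05, 52 weeks. Assume constant hazards and 52 weeks of follow-up for all.

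- Placebo relapse hazard: −ln(0.81)/26 = 0.00810 per week. Rapastinel: 0.475 × 0.00810 = 0.00385. Dropout: −ln(0.80)/26 = 0.00858.
- Expected events = 200 × λ/(λ+δ) × [1 − exp(−52(λ+δ))], with λ the relapse and δ the dropout hazard: 56.3 on placebo and 29.5 on rapastinel, 85.8 in total.
- Freedman: z = √85.8 × (1 − 0.475)/(1 + 0.475) − 1.96 = 3.30 − 1.96 = 1.34, power 91%.

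The stated 90% is reproduced without a covariate. If follow-up is staggered (assumed 26 weeks plus a uniform 0 to 65, capped at 52), about 79 events are expected and simulated log-rank power is still 90.3% with a non-prognostic covariate. Simulated type I error of the log-rank test is 5.1 to 5.2%.

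**2. How far could chance imbalance move the HR?** The SAP gives no prognostic strength for baseline MADRS, so assume a relapse HR of 1.25, 1.5 or 2.0 per SD. The standard error of the difference in baseline means, in SD units, is √(2/200) = 0.1, so a 1.96-standard-error imbalance is 0.196 SD. The factor on the HR is (HR per SD)^0.196.

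| HR per SD | Factor at 1.96 SE | Median shift (simulated) | Correlation of log HR with imbalance | Squared |
|---|---|---|---|---|
| 1.25 | 1.04 | 1.015 | 0.10 | 1% |
| 1.5 | 1.08 | 1.03 | 0.16 | 3% |
| 2.0 | 1.15 | 1.06 | 0.27 | 7% |

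The last column is the share of the log HR's variance that goes with imbalance. The whole 95% interval spans a factor of exp(1.96 × 0.2405) = 1.60 each way and already contains that share. Even in the roughly 5% of trials with imbalance beyond 1.96 standard errors, coverage of the unadjusted interval (around its own average) is 95.5%, 94.4% and 92.4%.

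**3. Would adjustment sharpen the estimate?** SD of the log HR, unadjusted against adjusted: 0.2405 and 0.2410; 0.2407 and 0.2422; 0.2417 and 0.2435. It does not fall. Power would change only if the adjusted test replaced the log-rank test: by 0.0, +0.8 and +3.6 points, and by −0.3 if the score is not prognostic. A supportive model makes no such replacement.

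**4. Would the gap between the two HRs measure imbalance?** The Cox HR is non-collapsible: conditioning on a prognostic covariate moves it away from 1 even when the arms are balanced.

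- Average HR, unadjusted against adjusted: 0.479 and 0.471 at 1.5 per SD (ratio 1.017); 0.493 and 0.470 at 2.0 (ratio 1.05).
- Trials with imbalance below 0.02 SD still show average gaps of about 1.005, 1.015 and 1.045.
- The gap points the opposite way to the actual imbalance in about 18%, 20% and 25% of trials.

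The median shifts in step 2 were obtained after subtracting the average gap over many simulated trials. The reader of one trial cannot do that.

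**5. Is the strongest case realistic?** Scores at entry lie between 0 and 12. With an assumed SD of 3 to 3.7 (a uniform spread gives 3.7), HR 2.0 per SD implies a relapse hazard 2^(12/3.7) ≈ 9 to 2^(12/3) = 16 times higher at 12 than at 0. The lower rows are the more believable ones, and four of the five relapse criteria do not use the MADRS cut-off at all.

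**The case for a change.** The best case for the concern is that it asks for little. A baseline score on the same scale as a relapse criterion is a natural covariate, and naming it before unblinding prevents a selective choice later. Adjustment does remove the correlation between the estimate and the imbalance (from 0.10 to 0.27 down to about 0). In the most imbalanced trials it brings coverage back to 95.6 to 95.7%.

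Those points stand as far as they go: the model would be harmless, and some statisticians would include it. They do not show that the SAP states anything wrongly, contradicts itself or fixes anything badly. The clearest coverage loss, to 92.4%, occurs only under the implausible HR of 2.0 per SD and only in about one trial in twenty. The absence itself cannot be established either, because text following Section 8.2 is blacked out and the protocol is not at hand. Only the readable text can be said to lack such an analysis.

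**Conclusion.** The concern does not hold. The log-rank test and the treatment-only Cox model are valid for this unstratified randomised comparison, agree across Sections 8.1, 8.2, 15.11 and Appendix I, and support the planned 90% power.

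A supportive adjusted HR would alter no decision, narrow no interval and add no confirmatory power. Its remaining purpose, separating imbalance from treatment effect, is undermined by non-collapsibility. At an HR of 1.25 to 1.5 per SD, the typical shift from imbalance is 1.5 to 3%, against an interval of about 60% in each direction on the ratio scale.

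These sizes rest on assumed prognostic strengths, a normally distributed covariate, constant hazards and 79 to 86 events per comparison, depending on follow-up. The validity of the unadjusted analysis does not depend on the assumed prognostic strength. No change is needed.

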## 8.2 SECONDARY EFFICACY ANALYSIS

The secondary efficacy endpoint is the time to first relapse during the entire DBTP, defined as the number of days from the randomization date to the relapse date during the entire DBTP. For patients who did not meet the relapse criteria during the DBTP, their time to relapse will be censored at the time of completion or discontinuation from the study. The same analysis method for the primary endpoint will be applied to the secondary endpoint.

In order to control the overall Type I error rate for the primary and secondary hypotheses, the following sequential testing procedure will be implemented in the following order:

- 1) The comparison of time to relapse during the first 52 weeks between rapastinel 450 mg weekly and placebo
- 2) The comparison of time to relapse during the entire DBTP between rapastinel 450 mg weekly and placebo
- 3) The comparison of time to relapse during the first 52 weeks between rapastinel 450 mg biweekly and placebo
- 4) The comparison of time to relapse during the entire DBTP between rapastinel 450 mg biweekly and placebo

Each of the 4 hypothesis tests above will be implemented at the 2-sided 0.05 significance level. A given hypothesis test will be carried out only when each of the preceding hypothesis tests have concluded rejection of the null hypothesis at the 0.05 significance level. In the event a given hypothesis test fails to reject its null hypothesis at the 0.05 significance level, the conclusion for the subsequent hypotheses not tested is to not reject their respective null hypotheses. This testing strategy will control the overall Type I error rate at 0.05 significance level.

*REDACTED*

